8.2.2.6 Follow-up of Adverse Events

All AEs experienced by a patient, irrespective of the suspected causality, will be monitored until the event has resolved, any abnormal laboratory values have returned to baseline or stabilized at a level acceptable to the investigator, until there is a satisfactory explanation for the changes observed, or until the patient is lost to follow-up or event is unlikely to resolve.

Data and Safety Monitoring Board (DSMB)

To protect the interests of research subjects and ensure that they are not exposed to undue risk, this trial will be monitored by an independent DSMB, consisting of appropriate medical experts

with no formal involvement with the subjects or the investigation and will function independently of the Clinical Study Team.

The Blood and Marrow Transplantation DSMB meets on a quarterly basis to review all the SAEs (unblinded); the most frequent AEs (blinded aggregate data) and laboratory data of interest and will make recommendation to the study team regarding the safety aspect of the study. Based on the safety data, the DSMB may recommend that the trial be modified or stopped or may request an interim analysis for efficacy.

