3. OVERALL DESIGN AND PLAN OF THE STUDY

3.1 Overview

This is a Phase II randomized, open-label study to evaluate the efficacy of extracorporeal photopheresis (ECP) versus IVMP on disability progression in subjects with SPMS. At the initial screening visit, an extensive medical history will be obtained and a detailed neurological examination will be performed to determine eligibility. Subjects who meet eligibility criteria will be enrolled in one of two study arms. Subjects will be randomized at a 1:1 ratio to receive ECP (study arm) or active treatment with intravenous methylprednisolone pulses (control arm) administered every 4 Weeks (1 gram per infusion) for 52 weeks.

ECP will be administered according to the following schedule:

Study Arm: Weeks 1-8: 3 times per week

Weeks 9-16: Twice per week

Weeks 17-36: Treatment on two consecutive days every 2 weeks (or optionally, one treatment per week)

Weeks 37-43: Once every 2 weeks

Weeks 44-52: Once every 4 Weeks

[figure not shown]
All subjects, including patients who receive corticosteroids, will be evaluated using the MSFC tool at baseline and every 3 months through 2 years (See Section 9.1 for timing of the schedule of assessments). They will also be scored using the EDSS at baseline and every 3 months through 2 years. Subjects in the control arm will be evaluated by MSFC and EDSS during the week prior to their next intravenous methylprednisolone infusion. Blood will be collected for immune function (cytokines) testing at baseline, and months 3, 6, 9 and 12. MRI will be done at baseline as well as months 6 and 12 following initiation of treatment; if the disability measurements are stable or improved at any point in time, then ECP will be continued per protocol..

Patients in the ECP arm should have all of their treatments with the CELLEX[®] System. Patients randomized to the ECP arm must receive their treatment within 5 days of baseline visit.

In the ECP process, UVADEX[®] (methoxsalen) Sterile Solution will be injected directly the recirculation bag of the extracorporeal circuit after completion of the buffy coat collection. The dose of UVADEX[®] (methoxsalen) Sterile Solution will be calculated based on the standard treatment volume formula (See Section 6.2).

For the schedule of assessments, please refer to Section 0.

Figure 1: Study Design

ECP=Extracorporeal Photopheresis MRI: Magnetic Resonance Imaging

¹ Frequency of ECP treatments:

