5. PATIENT WITHDRAWAL AND REPLACEMENT

Patients may withdraw from the study at any time without penalty and for any reason without prejudice to his or her future medical care.

Patients must be withdrawn under the following circumstances:

- The patient withdraws consent
- Pregnancy (see Section 8.2.2.9)
- Unacceptable toxicity including patients on corticosteroids who develop psychosis or aseptic necrosis of the femoral head

Patients may be required to withdraw after discussion with the investigator for the following reasons:

- AE(s)
- At the discretion of the investigator
- Violation of eligibility criteria
- Deviation from the treatment plan specified in the protocol (e.g., incorrect administration of the study drug, failure to attend study visits, etc.)
- The treating physician can withdraw the patient from the study at any time and for any medical reason that he/she deems necessary
- The patient has a right to withdraw at any time, for any medical or other reasons.
- Patients who experience a clinical relapse (defined as neurological event characterized by new or worsening symptoms lasting 48 hours after a stable period of at least 30 days and is considered in the judgment of the investigator to be a clinical relapse). Patients who fail therapy will be off study, and further therapy will be at the discretion of the treating neurologist. The study will not cover any form of therapy after the patient is off study.
- Patients who have interval accumulation of T1 or T2 lesions and/ or gadolinium enhancing T1 lesions on the month 6 MRI scan
- In all cases, the reason(s) for withdrawal, and the primary reason, must be recorded on the case report form (CRF) or similar.

Withdrawn patients will be replaced.

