10.1 Planned Sample Size and Number of Study Centers

It is planned to recruit approximately 66 patients (33 per treatment arm). This is a single center study.

Patients will be randomized on a 1:1 basis to corticosteroids or ECP arm.

Patients randomized to the ECP treatment arm must receive their first treatment within 5 days of the baseline visit.

For the randomization of patients, the investigator will use an Interactive Voice Response System (IVRS). Details can be found in the trial master file. IVRS will assign patients to a treatment group based on the pre-defined randomization list.

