10.3 Safety Analyses

Safety parameters for each patient include vital signs, laboratory testing, including chemistry panel and complete blood count, and AE reporting, including AEs resulting from active concomitant standard of care medication. These parameters will be tabulated in line listings along with basic demographic information such as sex and age by clinical site and by treatment arms.

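### The DSMB's routine package shows AEs not classed as serious only as blinded aggregates of the most frequent events, so the board cannot see an arm imbalance among them

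*Combined protocol and SAP*

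**What the plan says.** Section 8.2.2.6 sets up an independent board with no formal involvement with the subjects or the investigation and gives it three inputs:

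- Serious events: the board "meets on a quarterly basis to review all the SAEs (unblinded").
- Other events and laboratory results: "the most frequent AEs (blinded aggregate data) and laboratory data of interest". No cut-off for frequency is given, and the term for the masked data is not defined. No blinding status is attached to the laboratory data.

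On this basis "the DSMB may recommend that the trial be modified or stopped or may request an interim analysis for efficacy".

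Other relevant places:

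- Section 3.1: "This is a Phase II randomized, open-label study to evaluate the efficacy of extracorporeal photopheresis (ECP) versus IVMP".
- Section 5 makes withdrawal mandatory for "Unacceptable toxicity including patients on corticosteroids who develop psychosis or aseptic necrosis of the femoral head", and lists AEs among the reasons for which withdrawal may be required. Withdrawals are not among the board's inputs.
- Section 8.2.2.7 sends fatal or life-threatening SUSARs to regulators and ethics committees within 7 days, and UADEs to the FDA. It does not name the DSMB.
- Section 10.2.2 summarises the proportions with AEs and SAEs by treatment group, and 10.3 lists safety data "by clinical site and by treatment arms". Neither is described as a DSMB report, and neither gives a timing.

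**The concern.** A safety board compares arms. Here it can do so for serious events but, on the natural reading, not for the rest.

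Much of the toxicity that the protocol expects falls in that remainder. For ECP, Sections 3.3 and 7.1.1 name fever, blood pressure changes, nausea, malaise, hypotension and venous access problems. For corticosteroids, Appendix 3 names mood change, insomnia and reduced carbohydrate tolerance. Many such cases would not meet the SAE criteria in 8.2.2.3.1. Under 8.2.2.3.2 an AE can be graded severe because it prevents usual activities and still not be serious. Infection is plausible in both arms (Appendices 3 and 4), so a pooled infection count cannot be attributed to either treatment.

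The masking has no evident purpose. Patients and investigators know the arm, the board is separate from the study team, and it already sees SAEs unblinded.

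The plan has no planned interim efficacy analysis (10.2.3) and no numerical stopping rule, so independent oversight of tolerability depends on what this package contains. Section 1.2 describes a more frequent and prolonged schedule than in earlier studies. Withdrawals for AEs matter twice, because Section 10.2.1 counts early drop-outs as non-responders.

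**Working it through.** The documents give no figure for the board's review, so there is none to reproduce. The check has three parts.

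**1. What a pooled count can show.** Section 10.1: "It is planned to recruit approximately 66 patients (33 per treatment arm"). Suppose 13 patients in all have a given AE (an assumed count, at full enrolment). The board reads 13/66 = 19.7% whatever the split.

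| Split (of 33 and 33) | Arm rates | Pooled rate shown | Two-sided Fisher p |
|---|---|---|---|
| 6 v 7 | 18.2% v 21.2% | 19.7% | 1.0 |
| 3 v 10 | 9.1% v 30.3% | 19.7% | 0.061 |
| 0 v 13 | 0% v 39.4% | 19.7% | 0.000056 |

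The last row can be done by hand. The two equally extreme tables give p = 2 × C(33,13)/C(66,13) = 2 × 573,166,440 / 20,448,884,000,160 = 0.000056.

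Smaller totals behave the same way: 8/66 = 12.1% fits 4 v 4 (p = 1.0) and 8 v 0 (p = 0.005).

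**2. What a most-frequent list can show.** For an event with true rate r in one arm of 33, the expected count is 33r and the chance of at least one case is 1 − (1 − r)^33. The rates are assumptions.

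| r | Expected cases | P(at least one) |
|---|---|---|
| 1% | 0.33 | 28% |
| 2% | 0.66 | 49% |
| 3% | 0.99 | 63% |
| 5% | 1.65 | 82% |

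One or two cases are unlikely to rank among the most frequent AEs. If such a case is classed as serious, it reaches the board anyway; if not, it can be left off.

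**3. What the board receives, place by place.**

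| Information | Reaches the board routinely? |
|---|---|
| SAEs | Yes, unblinded, quarterly (8.2.2.6) |
| Frequent AEs not classed as serious | Only as a blinded aggregate (8.2.2.6) |
| Infrequent AEs not classed as serious | Not listed |
| Laboratory data of interest | Yes; blinding not stated (8.2.2.6) |
| AEs leading to withdrawal, as a group | Not listed (5, 8.2.2.6) |
| Fatal or life-threatening SUSARs, and UADEs, when sent to regulators | DSMB not named (8.2.2.7) |

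On the last row: such events are serious, so the board would see them at its next quarterly meeting. In 13 weeks a newly started ECP patient is scheduled for 8 × 3 + 5 × 2 = 34 sessions (Section 6.2).

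**Limit of by-arm review.** At 33 per arm, two-sided Fisher power at the 5% level is about 51% for 5% v 25%, 70% for 5% v 30% and 84% for 5% v 35%. By-arm tables would therefore support judgement; they would not replace it.

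**The case against.** The strongest reply is that the serious end is already covered. All SAEs reach the board unblinded, and the definition in 8.2.2.3.1 includes significant disability and important medical events. A reader might infer that the board cannot see psychosis or femoral-head necrosis. The documents do not support that: a case escapes only if it is judged non-serious. This stands, and it limits the point to events not classed as serious.

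A reader might also infer that an imbalance stays hidden until the end of the trial. That does not follow either. Investigators know each patient's arm and assess causality against ECP or corticosteroids (8.2.2.3.3). ECP technicians record events during procedures (8.2.2.4), SAEs are reported within 24 hours (8.2.2.5), and the Sponsor-Investigator can end the trial for a hazard (11.10). What is missing is the independent board's own view of the comparison.

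Four further replies have some force:

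- Laboratory data are a separate input with no blinding stated, and glucose is a listed parameter (8.2.3), so hyperglycaemia may be visible by that route.
- Blinded aggregate is undefined. Masked A and B columns are not excluded, although pooled is the natural reading. The ambiguity itself needs removing.
- Nothing bars the board from asking for more, although the only request named is an interim efficacy analysis. That named power also means that detecting harm is not its sole stated role.
- Some events, such as ECP access problems, reveal their arm by their nature.

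The last objection concerns the remedy. Sections 11.1 to 11.4 place data handling with the investigator's team and name no independent preparer of board reports. Splitting tables by arm without settling this could put accumulating comparative data before the people who treat and score patients. The fix has to deal with that.

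**Conclusion.** The point holds for AEs not classed as serious, within the DSMB's routine quarterly package. For these the board gets masked aggregates of the frequent events, and in an open-label trial the masking protects no blind. An imbalance as large as 0 v 13 would look the same as 6 v 7, and a rare toxicity judged non-serious could be left off. AEs leading to withdrawal are not listed for the board, and the expedited-reporting section does not name it.

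This rests on reading blinded aggregate as pooled over arms, and on the absence of fuller DSMB operating rules from the documents. The event counts and rates are illustrative, at full enrolment; early meetings would have fewer patients. The point is not that the trial as a whole is unaware of such events. It is a cheap improvement.

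**What to change.** In Section 8.2.2.6, replace "the most frequent AEs (blinded aggregate data) and laboratory data of interest" with: all AEs by system organ class and intensity, laboratory data of interest, and AEs leading to withdrawal, each by treatment arm with number treated as denominator, in a closed report prepared by a statistician or data manager not involved in treating or assessing patients.

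Add to 8.2.2.6 or 8.2.2.7 that fatal or life-threatening SUSARs, and UADEs, are copied to the DSMB chair when they are sent to the regulator.

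Cost: no new data or visits. The closed tables become somewhat longer, because they cover all AEs and withdrawals. Someone outside the treating and assessing team must be named to prepare them, and care is needed to keep comparative safety data within the board. The expedited reports gain one recipient.

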8.2.2.7 Suspected Unexpected Serious Adverse Reactions

Any AE that is serious, associated with the use of the study drug, and unexpected (defined as the nature or severity of event, which is not consistent with the applicable product information [i.e. Investigator's Brochure]) (SUSARs) has additional reporting requirements, as described below.

- If the SUSAR is fatal or life-threatening, associated with the use of the study drug, and unexpected, regulatory authorities and ethics committees will be notified within 7 calendar days after the Sponsor learns of the event. Additional follow-up (cause of death, autopsy report, and hospital report) information should be reported within an additional 8 days (15 days total).
- If the SUSAR is not fatal or life-threatening but is otherwise serious, associated with the use of the study drug, and unexpected, regulatory authorities and ethics committees will be notified within 15 calendar days after the Sponsor learns of the event.

The Sponsor will notify the investigators of relevant information about SUSARs that could adversely affect the safety of patients in a timely fashion. Follow-up information may be submitted if necessary.

The Sponsor will also provide annual safety updates to the regulatory authorities and ethics committees responsible for the trial. These updates will include information on SUSARs and other relevant safety findings.

Unanticipated Adverse Device Effects (UADE)

An unanticipated adverse device effect (UADE) means any serious adverse effect on health or safety or any life-threatening problem or death caused by, or associated with a device, if that effect, problem, or death was not previously identified in nature, severity, or degree of incidence in the investigational plan or application, or any other unanticipated serious problem associated with the device that relates to the rights, safety, or welfare of the subjects.

UADEs will be reported to the FDA as outlined nad required under 21 CFR p812.150(b)(1).

8.2.2.8 Pregnancy

The Sponsor has a responsibility to monitor the outcome of pregnancies where there has been maternal exposure to the investigational drug.

Pregnancy alone is not regarded as an AE unless there is a suspicion that the investigational product may have interfered with the effectiveness of a contraceptive medication.

Elective abortions without complications should not be handled as AEs, unless they were therapeutic abortions (see below). Hospitalization for normal delivery of a healthy newborn should not be considered a SAE.

All pregnancies must be reported by the investigator to the FDA on the initial pregnancy report form within 30 days after becoming aware of the pregnancy. The investigator must follow up and document the course and the outcome of all pregnancies even if the subject was discontinued from the study or if the study has finished.

All outcomes of pregnancy must be reported by the Sponsor-Investigator to the FDA on the pregnancy outcome report form within 30 days after he/she has gained knowledge of the normal delivery or elective abortion.

Any SAE that occurs during pregnancy must be recorded on the SAE report form (e.g., maternal serious complications, spontaneous or therapeutic abortion, ectopic pregnancy, stillbirth, neonatal death, congenital anomaly, birth defect) and reported within 24 hours in accordance with the procedure for reporting SAEs.

If a spouse of a male study subject who has been exposed to the Investigational Medicinal Product becomes pregnant, every effort should be made to monitor the pregnancy and outcome of pregnancy. A separate informed consent will be provided for the spouse prior to any data being collected regarding the pregnancy.

8.2.2.9 Complaint Reporting/Device Malfunctions

All device malfunctions should be reported to Therakos' support Hotline. The customer technical support phone numbers are [contact] in the US. Dialer should identify his/her involvement in this clinical study.

Device malfunctions do not have to be recorded in the CRF. Any AEs resulting from the malfunction will be reported in the CRF per Section 8.2.2.

8.2.3 Laboratory Parameters

Clinical laboratory assessments will be performed by the UM Hospital Clinical Laboratory at the University of Michigan. Research laboratory studies to measure immunological parameters will be conducted the Neuroimmunology Research Laboratory in the Department of Neurology at the University of Michigan ([name], Director).

Blood samples should be taken using standard venipuncture techniques. Blood samples should be processed according to the procedure described in the laboratory manual.

Laboratory parameters will be determined in accordance with the Schedule of Assessments on Table 2.

Table 1: Laboratory Assessments

Hematology:	Complete CBC
Chemistry:	Creatinine Glucose Triglycerides Urea Uric acid Bilirubin Cholesterol Sodium Potassium
Liver Function Tests	Alkaline phosphatase Aspartate transaminase Alanine transaminase
Immune Parameters	Myelin basic protein –specific IFN γ or IL-17 producing PBMC, Frequency of tetanus toxoid –specific IFN γ or IL-17 producing PBMC, plasma levels of IFN γ , IL-17, IL-4, IL-10, IL-12, IL-21, IL- 23, CCL2, GRO α , CXCL8, CXCL10, CCL11, CXCL13, GM-CSF, G-CSF and neutrophil elastase

Clinically significant laboratory abnormalities should be recorded as AEs according to investigator's judgment. The maximum total amount of blood that will be taken during the study from an individual patient for research studies is 60 ml per blood draw. There will be a total of five blood draws, separated by intervals of 9 weeks or longer. Patients on ECP will have an additional blood draw of 5 ccs prior to every procedure to determine hematocrit and platelet count.

8.2.4 Vital Signs

The following vital signs will be assessed in accordance with the Schedule of Assessments (Table 2):

- Weight and Height (height will be measured only at Screening);
- Blood pressure (systolic and diastolic; mmHg);
- Heart rate (beats per minute);
- Body temperature (°C);
- Respiration rate (breaths per minute).

These variables should be collected after the patient has been sitting for 5 minutes.

8.2.5 *Physical Examinations*

A brief physical examinations will be performed in accordance with the Schedule of Assessments (Table 2).

8.2.6 *Medical History and Interim History*

A complete medical history will be performed at start of study and a briefer interim history performed at each visit.

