7.1.1 UVADEX[®] (methoxsalen) Sterile Solution

The active ingredient in UVADEX[®] (methoxsalen) Sterile Solution is 8-methoxypsoralen (methoxsalen). Methoxsalen is a naturally occurring photoactive substance found in the seed of the Ammi majus (umbelliferae plant). It belongs to a class of compounds known as psoralens or furocoumarins. The chemical name is 9-methoxy-7H-furo[3,2-g][1]-benzopyran-7-one. The formulation of the drug is a sterile liquid at a concentration of 20 mcg/mL in a 10 mL vial. A complete description of the pharmacokinetic activity of methoxsalen is available in the Investigator's Brochure.

Systemic exposure to UVADEX[®] (methoxsalen) Sterile Solution following ECP is minimal. The total dose of methoxsalen used to inoculate these cells is less than 1/200th of the oral dose used in conjunction with the UVAR XTS[®] System. Plasma levels obtained as part of other clinical studies have shown no detectable level (<10 ng/mL) 30 minutes after the reinfusion of the treated cell suspension containing the UVADEX[®] (methoxsalen) in >75% of patients.

Adverse events associated with the ECPs process during CTCL clinical trials include venous access complications, transient fever and worsening of the underlying CTCL skin rash and transient hypotension associated with hypovolemia. A complete description of the AEs documented in studies using UVADEX[®] (methoxsalen) Sterile Solution is provided in the Investigator's Brochure.

UVADEX[®] (methoxsalen) Sterile Solution is currently approved in the US, UK, Germany, and Austria for use in the palliative treatment of the skin manifestations of CTCL unresponsive to other therapies.

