9. STUDY CONDUCT

9.1 Schedule of Assessments

The schedule of assessments is shown in months, as it facilitates better comprehension, preventing potential errors, in the interpretation of the exact timing for each assessment. On the other hand, in order to facilitate integration with the weekly-based schedule of ECP, and also budget considerations, we use the following transformation between weeks and months when addressing the schedule of assessments:

- a- 3 months: Week 12 \pm 2 week
- b- 6 months: Week 24 \pm 2week
- c- 9 months: Week 36 \pm 2 week
- d- 12 months or 1 year: Week 52 \pm 1 month

The schedule of assessments is shown in Table 2.

Table 2: Schedule of Assessments

Procedures	Screening (-30days)	Baseline ⁵ (Week 2)	Month 3	Month 6	Month 9	12 months/1year	Til End of Study (every 3 months through 2 years) ⁸
Informed Consent	X						
Inclusion/Exclusion Criteria	X						
Vital Signs		X	X	X	X	X	
Medical History/ Interim History ¹	X	X	X	X	X	X	
Physical Examination		X	X	X	X	X	
MSFC ⁸		X	X	X	X	X	X
EDSS ⁸		X	X	X	X	X	X
MRI		X		X		X	
Pregnancy Test ²	X						
Immune Parameters Measurement		X	X	X	X	X	
Clinical Laboratory Tests ³	X	X				X	
Pre-study/Concomitant MedicationsMRI	X	XX	X	XX	X	XX	
Adverse Events	X	X	X	X	X	X	
Randomization to ECP ^{5,6} vs IVMP ⁷	X						

¹ Including history of MS, progression from RRMS to onset of SPMS. A complete history at start of study and interim history at each visit.

²For women of childbearing potential.

³ Both at screening and prior to each ECP procedure, a small amount of blood (2-4 teaspoons) will be drawn to evaluate CBC and chemistries.

⁴Subjects will be randomized at a 1:1 ratio to either ECP.or IVMP

⁵Patients should have ECP within 14 days of baseline visit.

⁶The frequency of ECP treatments will be:

Weeks 1-8: 3 x/ week

Weeks 9-16: 2x/week

Weeks 17-36: 2x/2 weeks

Weeks 37-43: 1x / every 2 weeks

Weeks 44-52: 1x/ every 4 Weeks

⁷ Corticosteroid is administered on a pulse basis and consists of 1 gram of methylprednisolone I.V. every 4 Weeks for 52 Weeks.

⁸These test will occur every three month through 2 years.

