- Before ECP on each day of treatment blood samples will be collected for the laboratory tests on Table 1 and sent to the University of Michigan laboratory to perform testing as described above.
- Patients admitted to the corticosteroid arm will receive a treatment once every month as stated above
- The following will also be performed at this time point:
 - Interim history, vital signs, physical exam.
 - Blood for immune parameters (sent to the UM Neuroimmunology Research Laboratory)

- MSFC
- EDSS
- Adverse Events
- Concomitant Medications

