Patients who use proper eye protection after PUVA therapy (oral methoxsalen) appear to have no increased risk of developing cataracts. The incidence of cataracts in these patients five years after their first treatment is about the same as that in the general population. Patients should be told emphatically to wear UVA absorbing, wrap-around sunglasses for twenty-four (24) hours after UVADEX[®] treatment. They should wear these glasses any time they are exposed to direct or indirect sunlight, whether they are outdoors or exposed through a window.

Information for Patients:

Patients should be told emphatically to wear UVA-absorbing, wrap-around sunglasses and cover exposed skin or use a sunblock (SP 15 or higher) for the twenty-four (24) hour period following treatment with methoxsalen, whether exposed to direct or indirect sunlight in the open or through a window glass.

Drug Interactions:

See **Warnings** Section.

Carcinogenesis, Mutagenesis, and Impairment of Fertility:

See **Warnings** Section.

Pregnancy:

Pregnancy Category D. See **Warnings** Section.

Nursing Mothers:

It is not known whether this drug is excreted in human milk. Because many drugs are excreted in human milk, caution should be exercised when methoxsalen is administered to a nursing woman.

Pediatric Use:

Safety in children has not been established. Potential hazards of long-term therapy

include the possibilities of carcinogenicity and cataractogenicity as described in the Warnings Section as well as the probability of actinic degeneration which is also described in the Warnings Section.

ADVERSE REACTIONS

Side effects of photopheresis (UVADEX[®] used with the THERAKOS[™] Photopheresis System) were primarily related to hypotension secondary to changes in extracorporeal volume (>1%). In study CTCL 3 (UVADEX[®]), six serious cardiovascular adverse experiences were reported in five patients (5/51, 10%). Five of these six events were not related to photopheresis and did not interfere with the scheduled photopheresis treatments. One patient (1/51, 2%) with ischemic heart disease had an arrhythmia after the first day of photopheresis that was resolved the next day. Six infections were also reported in five patients. Two of the six events were Hickman catheter infections in one patient, which did not interrupt the scheduled photopheresis. The other four infections were not related to photopheresis and did not interfere with scheduled treatments.

OVERDOSAGE

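### No vital signs are scheduled as study data at ECP sessions or steroid infusions, so session-related hypotension will be seen only if reported as an adverse event, with no required measured value behind it.

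*Combined protocol and SAP*

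**What the plan says.** Section 10.3 names the safety data to be listed by arm: "Safety parameters for each patient include vital signs, laboratory testing, including chemistry panel and complete blood count, and AE reporting". Tolerability and safety of ECP versus corticosteroids is a secondary objective (Section 2.2).

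Timing of vital signs is set in Section 8.2.4 ("The following vital signs will be assessed in accordance with the Schedule of Assessments (Table 2"), with the condition "These variables should be collected after the patient has been sitting for 5 minutes". Section 9.1 confirms that "The schedule of assessments is shown in Table 2". Its vital-signs row is marked at baseline and months 3, 6, 9 and 12, and no footnote adds treatment-day readings. The by-visit text in Section 9.2 agrees: each visit from month 3 to week 52 lists "Interim history, vital signs, physical exam".

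The expected effect of ECP on blood pressure is also documented. Section 7.1.1 includes "transient hypotension associated with hypovolemia" among the events seen in the lymphoma trials. The label in Appendix 4 says that side effects of photopheresis "were primarily related to hypotension secondary to changes in extracorporeal volume". Section 3.3 mentions blood pressure variation in a cited series of 71 patients.

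For the control arm, Section 3.1 states: "Subjects in the control arm will be evaluated by MSFC and EDSS during the week prior to their next intravenous methylprednisolone infusion".

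**The concern.** A fall in blood pressure caused by moving volume out of the body is expected around the session. A seated resting value once a quarter is not placed to show it. The plan does specify treatment-day data where it wants them: Section 8.2.3 and footnote 3 of Table 2 require blood before each ECP procedure. Blood pressure, the variable most directly tied to the procedure, is not among them.

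The tolerability comparison for this effect therefore rests on adverse event reporting alone. The adverse event definition (8.2.2.2) gives no blood pressure threshold, and intensity (8.2.2.3.2) is graded by interference with usual activities. Falls that cause no symptoms, falls that nobody reports, and the size of any fall are lost. Ascertainment may also differ by arm. Section 8.2.2.4 names the technician as observer at every ECP procedure but names nobody at infusions. In an open-label trial, part of any difference in event counts could reflect who was watching.

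**Working it through.** The plan gives no figure on this point to reproduce. The check counts scheduled readings against planned treatment occasions.

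**ECP sessions per patient**
- Weeks 1-8, three per week: 8 × 3 = 24
- Weeks 9-16, two per week: 8 × 2 = 16
- Weeks 17-36, two every 2 weeks: (20 / 2) × 2 = 20
- Synopsis, weeks 37-44 every 2 weeks and 45-52 every 4 weeks: 4 + 2 = 6
- Synopsis total: 24 + 16 + 20 + 6 = 66
- Sections 3.1 and 6.2 divide the last phases at weeks 37-43 and 44-52, which gives 3-4 plus 2-3 sessions and a total of 65-67. The synopsis and body schedules need reconciling, but the difference does not affect this point.

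**Infusions per patient** (Section 6.1): 52 / 4 = 13, or 14 if both week 0 and week 52 are counted.

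**Vital-sign readings required because of a treatment:** 0 in either arm.

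**Most that could coincide with a treatment by chance of scheduling**
- ECP: four post-baseline visits, 4 / 66 = 6.1% (6.0-6.2% over 65-67 sessions). If the first session were also given on the baseline day, 5 / 66 = 7.6%. Neither case requires the reading to be taken at any set time relative to the procedure.
- Infusions: 4 / 13 = 31% (29% if 14). This is an upper bound. Table 2 puts vital signs at the same visits as MSFC and EDSS. If vital signs follow the Section 3.1 timing for those tests, they fall about 3 to 4 weeks after the last infusion.

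**Why a lowest-value table would mislead**
- Before-and-after readings give 66 × 2 = 132 per ECP patient and 13 × 2 = 26 per control, a ratio of 132 / 26 = 5.1.
- With independent normal readings and no treatment effect, the expected minimum is about -2.6 SD for 132 readings and -2.0 SD for 26. The ECP arm would appear to have lower blood pressure by about 0.6 SD from the count alone.

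**The case against.** The strongest reply is that the safety output does not depend on vital signs alone. The ECP technician must record any adverse event during the procedure. The definition of an adverse event covers signs as well as symptoms. Each report carries onset, resolution, intensity, treatment and relationship, and Section 10.3 lists adverse events. This stands: hypotension recognised as an event would appear. A reader might infer that the safety tables cannot show these changes at all, and the documents do not support that.

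Three further replies also stand.
- Appendix 3 lists hypertension, fluid retention and blood pressure elevation for corticosteroids, but never calls them transient or tied to the infusion. A sustained rise could show in the quarterly readings. A reader might infer that the quarterly values would look normal in both arms whatever happened, and this is not established.
- Nothing prevents a quarterly visit from falling on an ECP day, and the week-before rule in Section 3.1 names MSFC and EDSS only. Zero coverage is correct for required readings but not for possible ones.
- The documents do not say that the apheresis or infusion unit takes no readings. They only do not make such readings study data, so it cannot be said that no measured value would exist behind an event.

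It can also be argued that fuller capture is a preference in a 66-patient phase II trial whose adverse event summaries are descriptive (10.2.2). That bears on how much weight the point carries. It does not answer the mismatch between the effect the plan names and the times at which it measures.

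**Conclusion.** The point holds in a limited form. The five scheduled resting readings are not placed to describe blood pressure around about 66 ECP sessions, where the documents expect hypotension. Such episodes will be visible only when judged and reported as adverse events, with no protocol-required value and with a per-procedure observer named in one arm only. The ECP arm carries the finding. Readings at infusions serve mainly to make the arms comparable.

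The number of episodes that would go unmeasured cannot be stated. Rates of 1-5% per session would give 22-109 episodes over 33 × 66 = 2,178 sessions, and a reader might be tempted to quote that range. It is an assumption only: the label's figure of more than 1% has no stated per-session denominator, and the 5% has no source in the documents. In the cited 71-patient series, 4 patients had any toxicity, all of it mild and reversible.

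This rests on the session counts above and on Table 2 being the full list of scheduled vital signs. It does not affect the primary analysis. It is a worthwhile, inexpensive improvement to the safety data.

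**What to change.** - **Section 8.2.4 and Table 2:** add blood pressure and heart rate before and after each ECP session and each methylprednisolone infusion as case report form items. Before-and-after values can miss a fall during the session, so also record the lowest reading where the unit already takes readings during it.
- **Section 10.3:** summarise by arm the pre-to-post change per treatment occasion, for example the mean per-patient change and the proportion of occasions with a change of prespecified size. Keep this separate from the quarterly resting values. Do not compare the lowest or highest value per patient between arms.

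The cost is data entry: about 66 pairs of readings per ECP patient and 13 per control. With 33 per arm that is 33 × 66 + 33 × 13 = 2,178 + 429 = 2,607 pairs. ECP sessions already have a technician present and a blood draw beforehand, and infusions already bring the patient in, so no visit is added. The change concerns data collection only and leaves the treatment schedules as they are.
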